#### 10.4.3 Analysis of the Secondary and Exploratory Endpoint(s)

Pharmacokinetic parameters ( $C_{max}$ ,  $T_{max}$  and  $AUC_{0-\infty}$ , the period of time from insertion that naltrexone plasma concentrations remain above 1.33 ng/mL) will be calculated using a non-compartmental approach. Naltrexone plasma profiles will be plotted graphically for each individual and the study group (concentration-versus-time profile).

Use of opioids, cocaine, marijuana, and alcohol for each day of the study will be determined based on results of urine toxicology and self-report. Proportion of days with substance use for each participant will be summarized.

#### 10.4.4 Safety Analyses

The frequency of AEs including wound site and inflammatory response rates will be recorded. Any SAEs, adverse drug reactions, and suspected unexpected serious AE will be collated for the combined group. Additionally, counts of the number of laboratory values that fall outside of the normal range will be used to assess safety.

### 10.4.5 Adherence and Retention Analyses

The percentage of participants that complete the desired number of follow up blood collection points will be calculated and presented with 95% confidence intervals.

## 10.4.6 Baseline Descriptive Statistics

Baseline characteristics will be calculated using mean, standard deviation, median, interquartile range, percentages and 95% confidence intervals (where appropriate).

#### 10.4.7 Planned Interim Analyses

#### 10.4.7.1 Safety Review

As per AE reporting, AEs will be collated and reviewed quarterly by the Safety Committee. This may include crude rates of type specific AEs; however, no formal interim analysis will be conducted.

#### 10.4.7.2 Efficacy Review

An interim analysis will be carried out once at least 10 participants have completed their Day 180 PK blood time point. Participants, who submitted at least 14 of 19 valid blood samples (including the Day 180 sample) and safety data will be evaluated whether or not they met the MEC criteria (naltrexone blood level above 1.33 ng/mL). The analyzed interim data will be used in the planning and design of a bioequivalence/safety study of the OLANI against a reference extended release naltrexone product.

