#### 4.2.3 Primary Efficacy Endpoint:

• Proportion of participants who tolerate OLANI and maintain blood level of naltrexone of at least 1.33 ng/mL at all collected time points to ≥180 day time point.

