#### 5.4 PARTICIPANT WITHDRAWAL OR TERMINATION

#### 5.4.1 Reasons for Withdrawal or Termination

- A participant may withdraw from the study at any time or for any reason without being obliged to divulge their reason for doing so to the investigators or clinic staff.
- A participant may be withdrawn from the study if there are unacceptable AEs, laboratory abnormality or any other medical condition or situation including distress due to effects of any study procedure or medication.
- A participant may be withdrawn from the study if in the opinion of the treating clinician the participant's interests are best served by withdrawing from the study.
- A participant may be withdrawn from the study if the participant meets an exclusion criterion (either newly developed or not previously recognized) that precludes further study participation.
- Participant will be withdrawn from the study if they fail the naloxone challenge test.

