#### 5.4.2.1 Participant Monitoring and Removal from Study

Medical staff will assess and communicate with the study PI the appropriateness for continuation in the research study on a continuous basis and will remove from the trial participants with significant clinical deterioration or noncompliance of a type which could be dangerous. Criteria for removal from the study will include:

1. Clinical deterioration which cannot be managed safely in the context of outpatient treatment. This would include a participant who becomes suicidal, or a participant

who goes on severe drug binges (including non-opiate drugs), endangering him/herself.

- 2. Elevation of liver enzymes > 3 times normal. The PI or a study physician is available 24 hours/day by phone and/or beeper in case of emergency.
- 3. Participant becomes pregnant. In case of incidental pregnancy, the participant will remain in the study and will be followed until the resolution of pregnancy. To reduce unnecessary procedures, we will stop PK blood draws, unless clinically indicated, however the safety monitoring will continue. In addition, we will collect safety information related to the pregnancy and birth outcomes. After finding an incidental pregnancy the removal of the implant will be offered to the participant and the participant will decide how best to proceed in consultation with her obstetrician. The decision regarding the pregnancy will affect the decision whether or not to remove the implant at any point during the pregnancy. The risk of anesthesia differs during different times during pregnancy, however the risks of anesthesia and the risks of removal are both minimal.

If a participant becomes pregnant, PK labs will no longer be collected, but the participant will be followed for safety monitoring for the remainder of the study.

For those who withdraw from the study, (data collection and / or treatment) there are two main options:

- **Option 1:** Withdrawing from data collection and no further contact with study personnel. This carries the least amount of risk, with option 2 carrying some risk.

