#### 7.3.7 Early Termination Visit

Any participants that are withdrawn will be required to attend the SURC clinic for an early termination /withdrawal visit as outlined in Table 7-1. Participants will be advised of their options as outlined in in section 5.4.2.

A follow-up visit may be conducted 30 days after the last scheduled on-study visit and is required only if a participant has ongoing AEs or laboratory abnormalities at the last on-study visit. An in-clinic follow-up visit must be conducted 30 days after the last scheduled on-study visit for an AE requiring laboratory testing for participants with the following conditions at the last on-study visit: ongoing AEs, SAEs regardless of attributability, any laboratory abnormalities considered to be AEs or potentially harmful to the participant. For in-clinic follow-up visits, assessments performed should reflect what is considered medically necessary to assess the event(s).

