#### **10.3 ANALYSIS DATASETS**

The analysis will be performed based on Intention-to-Treat and Per-Protocol in all participants enrolled. Assessment of primary outcomes will be performed on participants who complete at least 75% of applicable time points.

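### The interim Day 180 review leaves out implanted participants who withdraw for intolerance before Day 180, so a 'tolerate and maintain' proportion read from it would be too high for such cases

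*Combined protocol and SAP*

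**What the plan says.** Section 4.2.3 (also in the Protocol Summary) defines the primary efficacy endpoint as a composite: "Proportion of participants who tolerate OLANI and maintain blood level of naltrexone of at least 1.33 ng/mL at all collected time points", up to Day 180 or later.

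The interim review in Section 10.4.7.2 starts once at least 10 participants have their Day 180 PK sample. It takes this set: "Participants, who submitted at least 14 of 19 valid blood samples (including the Day 180 sample) and safety data will be evaluated". The question asked of that set is "whether or not they met the MEC criteria (naltrexone blood level above 1.33 ng/mL". Tolerability is not part of the criterion. The results are to feed the planning of a bioequivalence/safety study.

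On early stopping:
- Section 5.4.1: "A participant may be withdrawn from the study if there are unacceptable AEs".
- Section 7.3.7: "Any participants that are withdrawn will be required to attend the SURC clinic for an early termination /withdrawal visit".
- Section 5.4.2.1, Option 1: "Withdrawing from data collection and no further contact with study personnel".
- Section 5.4.2 says who is not a treatment failure, but only for people who never received the implant.
- Section 7.3.8 answers dropout with extra recruitment and gives no scoring rule.

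For the final analysis, Section 10.3 gives Intention-to-Treat and Per-Protocol in everyone enrolled, and adds: "Assessment of primary outcomes will be performed on participants who complete at least 75% of applicable time points". Section 10.4.2 deals with the sample-collection endpoint. Section 10.4.3 deals with PK parameters and substance use.

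**The concern.** A participant who cannot tolerate the implant and withdraws before Day 180 has failed the first half of the Section 4.2.3 endpoint. Under the Section 10.4.7.2 rule that person is not in the set. A proportion taken from the set therefore omits a failure from its denominator, and for such cases the error runs one way, upward.

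The people planning the next study would be given this figure. At around 10 evaluable participants, one person visibly changes it. The word 'tolerate' is not defined anywhere, so without a rule stated in advance it would be interpreted after the data are seen.

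**Working it through.** **1. The plan's own count.** Section 3.1 lists 6 samples from 0 to 48 hours, 9 from Day 4 to Day 56, and 4 at Days 90, 120, 150 and 180. 6 + 9 + 4 = 19, which reproduces the denominator in Section 10.4.7.2. The 19 includes the 0-hour sample.

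**2. What excludes an early leaver.** With full sampling the 14th sample falls at Day 49 (6 hourly samples plus Days 4, 8, 14, 21, 28, 35, 42 and 49). Someone fully sampled who leaves after Day 150 has 18 of 19 and is still ineligible. For such a person the mandatory Day 180 sample does the excluding, not the count. Table 7-1 plans a PK draw at the early termination visit, but that does not replace a Day 180 sample when withdrawal comes well before it.

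**3. Effect of one omitted participant.** The documents give neither the share who meet the criterion nor the number of early intolerance withdrawals, so both are assumptions here. With share p met among n evaluable, adding one participant as not met changes the proportion from p to pn/(n+1), a fall of p/(n+1).

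| p | n = 10 | n = 15 | n = 19 |
|---|---|---|---|
| 50% | 4.5 points | 3.1 | 2.5 |
| 80% | 7.3 | 5.0 | 4.0 |
| 100% | 9.1 | 6.2 | 5.0 |

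With exact (Clopper-Pearson) 95% intervals, 8/10 = 80.0% (44.4 to 97.5) becomes 8/11 = 72.7% (39.0 to 94.0). The half-width at 8/10 is (97.5 − 44.4)/2 = 26.6 points.

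**4. The opposite direction.** The 14-sample minimum can also leave out participants who did meet the criterion. One or two such people would move 8/10 to 9/11 = 81.8% or 10/12 = 83.3%.

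**5. How likely is at least one case?** The only anchor in the documents is implant removal among 515 opiate treatments in the clinic review, which is a different population. Table 2-4 lists 5 removals for inflammatory response and 1 for another reason; Table 2-5 lists 1 for infection. Taken as separate treatments, that is 7/515 = 1.36%. P(at least one) = 1 − (508/515)^m, which is 12.8% for m = 10 implanted and 23.9% for m = 20. Removal is not the same as withdrawal, and the documents give no rate for other adverse-event withdrawals.

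**6. Scoring details left open.** Section 4.2.3 says at least 1.33 ng/mL; Section 10.4.7.2 says above it. The 0-hour sample is a listed time point, and Section 5.1 expects it to show zero naltrexone. Read literally, a requirement at all collected time points would fail everyone. No first scored post-dose time point is given.

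**The case against.** The strongest reply is that Section 10.4.7.2 never claims to estimate the composite endpoint. It checks the MEC criterion in evaluable participants, asks for safety data as well, and states no proportion. That stands: tolerability is unscored there, not redefined. A reader might infer that the plan has formally dropped intolerance failures from its primary efficacy endpoint, and the text does not support that.

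A reader might also infer that the final analysis has no population at all. Section 10.3 does give a general Intention-to-Treat and Per-Protocol basis. What is missing is detail: the sets are not defined, and it is not stated which one, or whether the 75% restriction, applies to this endpoint.

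Nor does implant removal by itself drop a participant. Section 4.1 plans PK collection in all participants, so someone followed after removal can still supply 14 samples including Day 180.

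Other outputs narrow the gap. Section 10.4.3 calculates time above 1.33 ng/mL and plots individual profiles, Section 10.4.10 tabulates individual data, and Section 8.1 reports discontinuations for adverse events. A reader could rebuild the proportion from these, but the plan does not say it will be reported that way.

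On materiality the objection is largely right. This is a single-arm pilot, Section 10.2 states no hypothesis, and no threshold is applied to the proportion. The difference between 'at least' and 'above' matters only for a value of exactly 1.33.

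**Conclusion.** The concern holds in limited form. The interim set leaves out implanted participants who withdraw for intolerance before Day 180, and any 'tolerate and maintain' proportion read from it is biased upward for those cases. The final analysis does not say which of its populations governs this endpoint or how early withdrawal is scored.

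The size rests on assumptions. At p = 80% and n = 10, one case costs 7.3 points; over p = 50% to 100% and n = 10 to 19 the range is 2.5 to 9.1 points. On the removal anchor, the chance of at least one case is 12.8% among 10 and 23.9% among 20. The effect may be nil, and it is small next to a half-width of 26.6 points.

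A reader might take the expected 50% completion in Section 5.3.1 to mean that up to ten intolerance failures could be hidden. That figure concerns completing the study with 75% of samples and two levels below 0.1 ng/mL. It is not a rate of intolerance before Day 180.

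The point is still worth fixing, because the interim data feed the design of the next study and the remedy uses data already collected.

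**What to change.** At interim and at final analysis, report the Section 4.2.3 proportion with an exact 95% CI among all implanted participants whose Day 180 window has closed at the data cut (Table 7-1 allows 10 days, so Day 190). Name this set in Section 10.3. Score as follows:

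- **Not met:** before Day 180, withdrawal for an adverse event, or removal or expulsion of the implant. Apply one relatedness criterion to both, stated in advance.
- **Not met:** any scored post-dose value below 1.33 ng/mL to Day 180. Do not score the pre-dose sample, and state the first scored post-dose time point in advance.
- **Bounds:** participants with no Day 180 result for other reasons (missed or remote visits, administrative loss, pregnancy) appear as best-case and worst-case limits. Pregnancy belongs here because Section 5.4.2.1 stops routine PK draws and says "After finding an incidental pregnancy the removal of the implant will be offered to the participant", so such a removal need not reflect intolerance.
- **Met:** the remainder, with a Day 180 result and no scored value below the threshold.

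Keep the 14-of-19 result as a sensitivity analysis, which also shows how much sparse sampling matters. Use the same threshold wording in Sections 4.2.3 and 10.4.7.2.

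The cost is one table from data already collected and a minor protocol amendment, which under Section 14.3 needs sponsor agreement and IRB approval. The proportion may come out lower, or as a range.

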#### 10.4.8 Additional Sub-Group Analyses

No sub-group analysis will be performed.

#### 10.4.9 Multiple Comparison/ Multiplicity

No adjustment will be made for multiple comparisons.

#### 10.4.10Tabulation of Individual Response Data

Individual pharmacokinetic and safety data will be tabulated for each time point and included in the appendices of the final study report.

#### 10.4.11Exploratory Analyses

No exploratory analysis will be conducted.

### 10.5 SAMPLE SIZE

At the completion of the study it is desirable that a minimum of 10 participants complete a minimum of 75% blood collection time points, including 2 consecutive undetectable values (defined as naltrexone blood levels of <0.1 ng/mL).

## **10.6 MEASURES TO MINIMIZE BIAS**

#### 10.6.1 Enrolment/ Randomization/ Masking Procedures

N/A as there is no blinding

#### 10.6.2 Evaluation of Success of Blinding

N/A as there is no blinding

## 10.6.3 Breaking the Study Blind/Participant Code

N/A as there is no blinding

#### 11 SOURCE DOCUMENTS AND ACCESS TO SOURCE DATA/DOCUMENTS

Direct access to source data/documents will be provided to the sponsor, trial-related monitoring, audits, NYSPI IRB, and regulatory inspection(s).

## **12 QUALITY ASSURANCE AND QUALITY CONTROL**

QC procedures will be implemented beginning with the data entry system and data QC checks that will be run on the database will be generated. Any missing data or data anomalies will be communicated to the site(s) for clarification/resolution.

Following written SOPs, the monitors will verify that the clinical trial is conducted and data are generated, documented (recorded) and reported in compliance with the protocol, GCP and the applicable regulatory requirements (e.g. Good Laboratory Practices (GLP), Good Manufacturing Practices (GMP).

The investigational site will provide direct access to all trial related sites, source data/documents and reports for the purpose of monitoring and auditing by the Sponsor, CRO (Clinilabs) and inspection by local and regulatory authorities.

## **13 ETHICS/PROTECTION OF HUMAN PARTICIPANTS**

#### **13.1 ETHICAL STANDARD**

The study will be conducted in accordance with the guidelines and principles outlined in the International Conference on Harmonization - Standards of Good Clinical Practice and the Declaration of Helsinki.Compliance with these standards ensures that the rights, safety and well-being of participants are consistent with the above principles.

#### **13.2 INSTITUTIONAL REVIEW BOARD**

The investigator will obtain NYSPI IRB approval for this study. Initial IRB approval as well as all materials approved by the IRB for this study, including the participant consent form and recruitment materials.

Annual Reports describing the study progress and all AEs will be provided to the NYSPI IRB, along with a final study report by the PI. A copy of this report will also be provided to the sponsor.

#### **13.3 INFORMED CONSENT PROCESS**

#### 13.3.1 Consent/Assent and Other Informational Documents Provided to Participants

All study participants will be provided with a Participant Information Sheet (PIS) describing the study and providing sufficient information so that they are able to make an informed decision about their participation in the trial. Both the PIS and the Participant Informed Consent (PIC) form will be submitted with the research application for review and approval by the IRB.

#### 13.3.2 Consent Procedures and Documentation

The investigator (or authorized designee) will ensure that the participant (or the participant's legal representative) is given full and adequate oral and written information about the nature, purpose, potential and possible risks and benefits of the study. Each prospective participant will receive an IRB-approved ICF that summarizes the pertinent study information and will be given ample time to read the form and ask questions about the study. All information is to be provided in a language understandable to the participant and must not include any language that waives the participant's legal rights. Prospective participants must also be informed of their right to withdraw consent without prejudice at any time during the study. If the participant chooses to participate, he/she must sign the ICF before any study-specific procedures are conducted.

### **13.4 PARTICIPANT AND DATA CONFIDENTIALITY**

All data generated in this study will remain confidential. All information will be stored securely. participant information will only be disclosed to authorized individuals i.e. research personnel listed on the Delegation of Duties List who have signed a confidentiality agreement with the PI to undertake research related procedures.

All participant data will be de-identified by use of an alphanumeric study coding system.

Participant identification will be recorded on a Master Participants List held in-confidence by the PI in a locked cabinet separate to the de-identified data sheets.

Personal information recorded in study documentation or an electronic database will only be accessed by authorized study personnel. Personal computer access will be password protected and also limited to authorized study personnel.

Additionally, a Federal Certificate of Confidentiality will be obtained.

### 13.4.1 Research Use of Stored Human Samples, Specimens or Data

## 13.4.1.1 Naltrexone blood level

Samples collected up to and including the 48 hour time point will be prepared by study personnel from NYSPI for storage at -70°C before shipment in batches to the PK analysis laboratory. Samples collected after the 48 hour time point will be processed by Clinilabs and stored until suitable batch sizes are available for shipment to the PK laboratory on dry ice. All samples will be analyzed for free (unconjugated) naltrexone and free (unconjugated) 6- $\beta$ -naltrexol quantification. It is anticipated that samples will prepared and split into 2 aliquots, with 1 being used for analysis and 1 serving as a backup being stored de-identified in a -70°C freezer. Samples will be kept for 5 years after the completion of the trial, after which time they will be destroyed.

## 13.5 FUTURE USE OF STORED SPECIMENS

Data collected for this study will be analyzed and stored at NYSPI, as per local standard protocols.

## 14 DATA HANDLING AND RECORD KEEPING

#### 14.1 DATA COLLECTION AND MANAGEMENT RESPONSIBILITIES

An electronic Case Report Form (eCRF) will be designed to record data required by the protocol and collected by the Investigator. An eCRF will be completed for each participant.

A confidential list of participant names, contact details, and screening numbers will be kept by the the Clinilabs and SURC clinics. eCRF data removed from the study site will be identified by the screening number and will not contain participant names or contact details.

Data collection is the responsibility of the clinical trial staff at the site under the supervision of the site PI. The investigator is responsible for ensuring the accuracy, completeness, legibility and timeliness of the data reported. All source documents should be completed in a neat, legible manner to ensure accurate interpretation of data.

#### **14.2 STUDY RECORDS RETENTION**

Retention and storage of essential clinical study documents (e.g. worksheets, drug accountability forms, and other administrative documentation) shall be governed by the terms and conditions of NYSPI.

- Ten years after discontinuation of the study, or
- Two years following the date a marketing application is approved for the study drug for the indication for which it is being investigated pursuant to the study, or
- If no application is to be filed or if the application is not approved for such indication, until 2 years after the date the study is terminated.

Participants' medical files should be retained in accordance with the applicable legislation and in accordance with the maximum period of time permitted by the hospital, institution, or private practice

